14.2. Analysis of Outcomes

A separate Statistical Analysis Plan will be produced and will provide a more comprehensive description of the planned statistical analyses. A brief outline of these analyses is given below.

The primary comparison groups will be composed of those randomised to manual rotation versus those randomised to instrumental rotation. In the first instance, all analyses will be based on the

intention to treat principle, i.e. all participants will be analysed in the intervention group to which they were randomised irrespective of adherence to randomised intervention or protocol deviations.

For all relevant outcomes, appropriate summary statistics and differences between groups be presented, with 95% confidence intervals and p-values from two-sided tests also provided. Intervention effects will be adjusted for the minimisation listed in section 6.3.2 where possible. No adjustment for multiple comparisons will be made.

14.2.1. Primary outcome

The co-primary outcomes of 3rd/4th degree perineal trauma and caesarean section will be analysed using mixed-effects log-binomial models to generate relative risks alongside risk differences with 95% confidence intervals, adjusting for the position as a fixed effect and centre as a random effect. If the log-binomial model fails to converge, a Poisson regression model with robust standard errors will be used to estimate the same parameters. If this also fails, unadjusted estimates will be produced from the log-binomial model.

We have not adjusted for Type II error, as we will not be considering a joint effect of both outcomes. Interpretation of the results will be based on the treatment effect and 95% confidence intervals for each outcome.

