5.2. Recruitment Process

- There will be ample **antenatal provision of information**. A large variety of strategies will be employed to enable this including leaflets in case notes and in antenatal clinics, social media campaigns, a study website, posters, newsletters and emails. Women attending antenatal clinics with elevated risk of operative birth will be targeted; for example, nulliparous women and women undergoing induction of labour. With this strategy, we aim for the vast majority of pregnant women to be aware of the study.
- There will be an opportunity to have any questions about the study answered by a midwife, doctor or researcher. This will be either directly, via a 'phone-back' service, social media or by email. If, following discussion, a woman decides that she does not want to take part, then she can **opt-out** by placing a small sticker on the inside cover of her file. The sticker will be replaced with a red flag in electronic notes. This sticker will be contained on all leaflets, which clearly state that women should attach the sticker to the inside cover of their case notes if they do not wish to be approached to participate in the study. **Digital flags** and other systems tested in practice via the HTA funded COPE RCT (EudraCT number: 2018-001829-11) will be used in units with electronic records. Women who decline, will be asked if they wish to participate in the qualitative interviews.
- The lay PPI panel has identified a potential issue: there is a wide perception in the community that forceps are dangerous, which might impede recruitment and randomisation as forceps is one of the interventions. Qualitative research during the pilot, with the support of PPI, will explore how best to provide **information to women about forceps** to help improve recruitment should this be identified as an issue within the trial.

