5.3 Consent process

Postnatally (prior to discharge, usually within 24-48 hours), a full patient information sheet will be provided to these women who verbally consented, and written consent will be sought for the use of data already collected, for participation in follow-up, and for participation in qualitative work (in the pilot) if applicable.

- Following informed verbal consent there will be automated telephone randomisation. Telephone randomisation has been shown to be efficient and pragmatic in several intrapartum trials in our experience. We have kept the number of minimisation factors to the minimum to enable an efficient and rapid randomisation process. Most of the clinicians in our national survey perform rotational deliveries in theatre which will increase the chances of recruiting – there is, in such deliveries, more time and more personnel available compared to deliveries in the labour ward room. In addition to telephone randomisation, we could also offer the option to randomise the patient via an internet-based portal. We have accounted for any missed opportunities in the very conservative estimates of recruitment rates (on average six women per site per month). Using an adaptive approach, we will monitor the randomisation process during the pilot period and amend as necessary based on the process evaluation.
- It will be the responsibility of the Principal Investigator (PI) to obtain written informed consent for each participant. This task can be delegated by the PI to other members of the local research team, most likely a Research Midwife, if local practice allows and this responsibility has been documented in the site signature and delegation log.

- Where a patient gives verbal consent and is randomised but does not give written consent anonymised data will be collected on the Day 0, 48 Hour Follow Up and Neonatal CRFs only (please see Section 5.3 for further details)
- Additional consent will be taken in the pilot for the **qualitative work** with women, partners, and healthcare professionals: interviews and audio recordings etc.

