14. STATISTICAL CONSIDERATIONS

14.1. Sample Size

Superiority: We meta-analysed results from 5 recent studies (16–18,32,33)to calculate a pooled estimate for the control group rate. The pooled incidence of third/fourth degree perineal trauma was 5% (95% confidence interval (CI) 2% to 7%). This is in line with the national REDEFINE audit (19), where the incidence was 6.6% for rotational forceps, 4.6% for rotational ventouse, and 4.3% for manual rotation. To detect a reduction of third/fourth degree perineal trauma from 6% to 4% (equivalent to a risk ratio of 0.67) with 90% power, 5% two-sided significance level using the standard method of difference between proportions and based on a superiority hypothesis, requires 4,988 women in total. We considered an incidence of 6% of perineal trauma, as this closely reflected the rates reported in the REDEFINE audit, and a 2% clinically relevant reduction after consultation with co-applicants. We anticipate drop out or loss to follow-up for this outcome to be low (around 4%) and will aim to recruit 5,200 women (2,600 in each group) to account for this. The sample size has been calculated according to the normal approximation to the binomial distribution. The trial is designed as a pragmatic study to provide real-world evidence, and as such, the sample size has been

calculated according to an intention-to-treat analysis, i.e. the primary analysis will be based on the group to which the woman was randomised whether or not she crossed-over. The number of women for whom cross-over to the opposite rotational method occurs is expected to be minimal (<1%), based on previous studies (0-0.6%) as detailed in the Analysis section, and will therefore have a negligible impact on the treatment effect. The degree of cross-over will be monitored closely. A sensitivity analysis excluding cross-overs will assess the robustness of the conclusions.

Non-inferiority: The pooled incidence for caesarean section in the meta-analysis, based on observational research, was 9% (95% CI 6% to 13%). We assumed a conservative estimate of 12% as the control group rate for this outcome.

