14.2.4. Exploratory analyses

A series of exploratory analyses will be conducted in which the co-primary outcomes and neonatal outcomes will be summarised by the following variables:

- instrument used (rotational forceps versus rotational ventouse)
- type of anaesthesia at randomisation
- parity (nulliparous/parous)
- baby's position (transverse/posterior)
- choice of method for completing birth after rotation.

For each of these exploratory analyses, summary statistics will be presented for each group and results will be treated with caution and will be used for the purposes of hypothesis generation only.

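### Both co-primary models omit parity, a pre-birth variable the protocol plans to hold: adding it is a small, nearly free gain, not the repair of an error

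*Protocol*

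**What the plan says.** Protocol section 14.2 sets a general rule: "Intervention effects will be adjusted for the minimisation listed in" section 6.3.2, which names centre and position (occipito-transverse or occipito-posterior). Section 14.2.1 applies the rule to perineal trauma and caesarean section, "adjusting for the position as a fixed effect and centre as a random effect". If the log-binomial model does not converge, a Poisson model with robust standard errors replaces it. If that fails too, the estimates are unadjusted.

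Parity enters the analysis only in section 14.2.4, in a list of exploratory variables, with this treatment: "For each of these exploratory analyses, summary statistics will be presented for each group". Section 14.2.3 restricts subgroup analyses to the minimisation variables.

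The short list of minimisation factors is explained in section 5.3 (Consent process): "We have kept the number of minimisation factors to the minimum to enable an efficient and rapid randomisation process".

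**The concern.** The reason given for having few minimisation factors is speed at the bedside. That is a good reason not to minimise on parity, but it does not bear on a regression fitted after follow-up. Parity cannot be changed by the allocated technique, and the protocol already intends to have it for tabulation. If it predicts either co-primary outcome, leaving it out makes the intervals slightly wider than they need be.

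A chance difference in parity between the arms would also stay in the primary estimate. This matters most for caesarean section, which is judged against a fixed 3.5-point margin. The trial is open-label, and a parity adjustment introduced only after an imbalance had been seen would be open to challenge. One prespecified beforehand would not.

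The last-resort fallback has a related weakness: it discards even the two minimisation factors because of a convergence problem.

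**Working it through.** **1. The plan's own figures (section 14.1).** The superiority calculation is "with 90% power, 5% two-sided significance level using the standard method of difference between proportions", for 6% against 4%.

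- Per arm: [1.960 × √(2 × 0.05 × 0.95) + 1.2816 × √(0.06 × 0.94 + 0.04 × 0.96)]² / 0.02² = 2,494. The total is 4,988, as stated. Allowing for 4% loss, 4,988 / 0.96 = 5,196, rounded to 5,200.
- Non-inferiority at 15% with a 3.5-point margin: 2 × 0.15 × 0.85 × (1.960 + 1.2816)² / 0.035² gives 2,188 per arm, or 4,376 in total, as tabulated. The other seven table entries also reproduce exactly.
- Power at 5,200 for that margin: 0.035 / √(2 × 0.15 × 0.85 / 2,600) − 1.960 = 1.574, which is 94.2%. For tears with 5,200 × 0.96 = 4,992 women analysed, power is 90.0%.

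**2. Assumptions not in the documents.** Nulliparous share q of 60-90%; nulliparous-to-parous risk ratio RR of 1.5-4. Overall risk p is 15% for caesarean and 5% for tears (the mean of 6% and 4%).

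**3. Formulae.**

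- Risk in parous women: p0 = p / (q × RR + 1 − q). Risk in nulliparous women: p1 = RR × p0.
- Share of variance explained: R² = q(1 − q)(p1 − p0)² / [p(1 − p)]. The variance of the treatment effect is multiplied by (1 − R²).
- Equivalent women: 5,200 × R².
- Shift from a 1.96-SD parity imbalance: 1.96 × √(2q(1 − q) / 2,600) × (p1 − p0).

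**4. One case in full.** Caesarean, q = 0.7, RR = 2: p0 = 0.15 / 1.7 = 0.088 and p1 = 0.176. R² = 0.21 × 0.0882² / 0.1275 = 1.28%. The shift is 1.96 × √(0.42 / 2,600) × 0.0882 = 0.22 points.

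**5. Range.**

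| Outcome | q, RR | R² | SE falls by | Power | Equivalent women | Shift (points) |
|---|---|---|---|---|---|---|
| Caesarean, 15% | 90%, 1.5 | 0.19% | 0.09% | 94.23 to 94.27% | 10 | 0.08 |
| | 70%, 2 | 1.28% | 0.64% | 94.23 to 94.49% | 67 | 0.22 |
| | 60%, 4 | 4.86% | 2.46% | 94.23 to 95.19% | 253 | 0.43 |
| Tears, 5% | 90%, 1.5 | 0.06% | 0.03% | 90.03 to 90.05% | 3 | 0.03 |
| | 70%, 2 | 0.38% | 0.19% | 90.03 to 90.14% | 20 | 0.07 |
| | 60%, 4 | 1.45% | 0.73% | 90.03 to 90.44% | 75 | 0.14 |

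At a 12% caesarean rate the gains are smaller: R² is 0.15-3.76%, and power goes from 97.3% to at most 97.7%.

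**6. Cross-check.** Robust Poisson models were simulated for tears, 2,000 runs per scenario. Adding parity took the standard error of the log relative risk from 0.1266 to 0.1264 (70%, RR 2), from 0.1266 to 0.1263 (80%, RR 3) and from 0.1265 to 0.1256 (60%, RR 4). The last is a 0.7% fall, in line with the table. The unadjusted estimate showed no bias.

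**7. Scale.** The half-width of the 95% interval for the caesarean difference is 1.96 × √(2 × 0.15 × 0.85 / 2,600) = 1.94 points. The largest shift, 0.43 points, is 12% of the margin (0.43 / 3.5) and about a fifth of that half-width.

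**The case against.** The strongest reply is that nothing here is wrong. The trial minimises on two factors and adjusts for the same two, which is standard and coherent. Section 14.2 calls itself an outline and defers to a separate SAP, which is not at hand and may contain a parity-adjusted supportive analysis. The gain rests on assumed values and is negligible for tears. This all stands, and it limits the point to a suggestion. It does not remove the point, because section 14.2.1 names the primary covariates and parity is not among them.

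Four stronger readings are tempting, and the documents do not support them.

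- **That omitting parity biases the result.** Allocation is randomised. Chance imbalance is not systematic bias, and its variability is already inside the confidence interval.
- **That the protocol itself shows parity to be prognostic.** Section 5.2 gives as examples of raised risk of operative birth "for example, nulliparous women and women undergoing induction of labour", but every woman randomised already needs such a birth. Section 1.2 reports a time trend in tears among first-time mothers, with no comparison with parous women. Neither gives a parity-specific risk of a co-primary outcome among enrolled women.
- **That parity is documented as a baseline item.** It appears neither in the schedule of assessments (section 9.1) nor in the list of data entered directly on the CRF (section 11.1). That it is known before randomisation follows from what parity is, not from anything the protocol states.
- **That parity and type of anaesthesia should have formal interaction tests.** Section 14.2.3 deliberately limits subgroups to the minimisation variables, and section 14.2 plans no multiplicity adjustment. Widening that list is a debatable trade-off, not a correction.

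**Conclusion.** This is a low-priority improvement. The primary models leave out a variable that the protocol plans to hold and that allocation cannot affect; the reason given for few minimisation factors does not extend to the models. The cost of the omission is small: at most about 1 point of power for caesarean section and 0.4 points for perineal trauma. A fairly extreme parity imbalance would move the caesarean difference by 0.08-0.43 points. The upper ends need a fourfold risk ratio with 40% of women parous. The trial meets its stated power without parity, and no planned conclusion is invalid. The sizes depend wholly on the assumed parity mix and risk ratios. If parity is only weakly related to the outcomes, the gain is close to nil and so is the loss from including it.

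**What to change.** In section 14.2.1, and correspondingly in the SAP, add parity (nulliparous/parous) as a fixed effect in both co-primary models, beside position and the random effect for centre. Confirm that the CRF records parity as its value before the index birth, so that this birth does not turn a nulliparous woman into a parous one.

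Replace the last fallback. If the log-binomial and Poisson models both fail, fit a logistic model with the same covariates and obtain the relative risk and risk difference by marginal standardisation. This keeps the adjustment and gives the absolute difference to which the 3.5-point margin applies.

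The cost is wording, plus the check that parity is captured. One more covariate slightly raises the chance that the log-binomial model will not converge, which the revised fallback covers. Sample size, randomisation and the subgroup list stay as they are.

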14.2.2. Secondary outcomes

Analysis will be performed as per the primary outcome for all binary secondary outcomes (e.g. successful vaginal birth, breastfeeding intention after birth) as well as any safety output (e.g. SAEs). For continuous outcomes (e.g. estimated blood loss), a mixed-effects linear regression model will be used to generate difference between group means and confidence intervals adjusting for the same minimisation parameters as the primary outcome.

14.2.3. Subgroup analyses

Subgroup analyses will be limited to the same variables used in the minimisation algorithm (see section 6.3.2) and performed on the co-primary outcomes. The effects of these subgroups will be examined by including an intervention group by subgroup interaction parameter in the regression model, which will be presented alongside the effect estimate and 95% confidence interval within subgroups. The results of subgroup analyses will be treated with caution and will be used for the purposes of hypothesis generation only.

14.2.4. Exploratory analyses

A series of exploratory analyses will be conducted in which the co-primary outcomes and neonatal outcomes will be summarised by the following variables:

- instrument used (rotational forceps versus rotational ventouse)
- type of anaesthesia at randomisation
- parity (nulliparous/parous)
- baby's position (transverse/posterior)
- choice of method for completing birth after rotation.

For each of these exploratory analyses, summary statistics will be presented for each group and results will be treated with caution and will be used for the purposes of hypothesis generation only.

14.2.5. Missing Data and Sensitivity Analyses

Every attempt will be made to collect full follow-up data on all study participants; it is thus anticipated that missing data will be minimal. Participants with missing primary outcome data will

not be included in the primary analysis in the first instance. This presents a risk of bias, and sensitivity analyses will be undertaken to assess the possible impact of the risk.

Per protocol, populations are 1) women having manual rotation as the first method, 2) women having instrumental rotation as the first method (regardless of instrument used). As we anticipate some cross-overs for participants having a failed attempt at rotation with one method to the other (instrumental rotation after failed manual rotation; and manual rotation after instrumental rotation), we will examine the robustness of the conclusions using appropriate sensitivity analyses including a per protocol analysis (i.e. restricting the analysis data set to those women who received the allocated intervention only) on the two co-primary outcomes. In two recent studies (16,17) the rate of cross-over was 0% after rotational forceps, and 0.6% (1/163) after manual rotation, representing a single case in one study (17). In the same study (17), although a second instrument was used in 36.9% of cases after rotational ventouse, this typically involved the use of forceps to complete the birth and therefore was not a cross-over from ventouse to manual rotation . Therefore, we expect the rate of cross-over between the two intervention groups to be very low – the 95% confidence interval for a rate of 1/163 is: 0.01 to 3.37%.

Full details will be included in the Statistical Analysis Plan.

14.3. Interim Analyses

Interim analyses of safety and efficacy will be presented to the independent DMC/Trial Oversight Committee during the trial. This is likely to include the analysis of the primary and major secondary outcomes and full assessment of safety (SAEs) at least at annual intervals. Criteria for stopping or modifying the trial based on this information will be ratified by the DMC. Details of the agreed plan will be written into a DMC Charter and the Statistical Analysis Plan. Further details of DMC arrangements are given in section 17.5.

14.4. Planned Final Analyses

The primary analysis for the trial will occur once all participants have completed the 3-month follow up assessment and corresponding outcome data has been entered onto the trial database and validated as being ready for analysis. This analysis will include data items up to and including the 3-month follow up assessment and no further.

15. HEALTH ECONOMICS

No Health Economic evaluation is planned for this trial.

16. SUB-STUDY 1: QUALITATIVE PROCESS EVALUATION

16.1. Aim

To qualitatively explore the feasibility, acceptability and appropriateness of the intervention and trial (including consent) processes for women and their birth partners, and healthcare professionals involved in delivering the pilot trial.

16.2. Objectives

1. With women: to explore their views and experiences of the recruitment approach, voluntariness, consent processes, randomisation, barriers and facilitators to participation, and acceptability of treatment allocations

With healthcare professionals: to explore their views and experiences of recruitment, consent processes, randomisation, including perceived barriers and facilitators, equipoise, appropriateness and acceptability of treatment allocations, and perceptions of trial processes.
 With partners: to explore their views and experiences of being present during the trial recruitment approach, and their perception of acceptability of treatment allocations

16.3. Outcomes

This pragmatic qualitative process evaluation is aligned with the MRC framework for evaluation of complex interventions (34). The primary outcome of the qualitative process evaluation is to explore the feasibility, acceptability and appropriateness of the trial and intervention for women, their birth partners and healthcare professionals (HCPs). The results will dynamically inform decision-making around progression to a full trial and study design and processes. In addition, the results may help to (a) inform improvements to NHS care for women with persistent malposition of the fetal head; (b) inform future national guidelines and compulsory obstetric training.

16.4. Methodological approach and theoretical positioning

The qualitative research will be guided by interpretive descriptive (ID) methodology.(35) ID is aligned with a constructivist and naturalistic orientation to inquiry (36), the purpose of which is to capture themes and patterns within subjective perceptions of experiences and generate an interpretive account capable of informing clinical understanding and decision making (37). This is directly aligned with the aim of the qualitative process evaluation within ROTATE. ID acknowledges the theoretical and practical knowledge that researchers bring to a study and clinical expertise is acknowledged as a useful starting place for orienting and designing the research particularly when the area of inquiry has yet to be evaluated rigorously (36) as is the case with malposition of the fetal head. Knowledge from a range of sources (e.g. current evidence base and clinical expertise) will form the theoretical scaffolding from which the researchers will undertake the qualitative inquiry within ROTATE and this will be challenged and refined as the research progresses (36,37).

